4.4.3 Additional Data

The following data will also be collected.

- Demographics: gender, age, ethnicity, race, cardiac disease history, arrhythmia history, indication for ICD implant, history of smoking, etc.
- Device electrical measurements at the MRI Scan Visit (before and after the scan) and at the 1 Month Post Scan Visit
- ADE, SADE, UADE/USADE
- Mortality

Clinical Investigational Plan

- Number of non-study related MRI scans
- Proportion of VT/VF episodes with significant detection delay assessed from device-detected VT/VF episodes (induced or spontaneous) with stored electrogram available
- Summarize number of subjects that returned to usual programming after the MRI scan and number of subjects, if any, experiencing delays in reprogramming

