12.2.5 Analysis

The dataset will be frozen for analysis when 141 subjects have completed the 1 month post MRI visit and a minimum of 25 subjects with at least one ventricular arrhythmia event (spontaneous or induced) are adjudicated by the Ventricular Arrhythmia Events Committee. If a minimum of 25 subjects have not experienced a ventricular arrhythmia event (spontaneous or induced) at this time, SJM will discuss progress of data collection for ventricular arrhythmia events with FDA to support the minimum requirements to support a pre-market approval (PMA) application.

Clinical Investigational Plan

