14.0 Study Committee

14.1 Clinical Events Committee (CEC)/Ventricular Arrhythmia Event Review Committee (VAC)

The CEC is responsible for providing an independent review and adjudication of CIP pre-defined clinical events. The CEC will consist of at least 3 members. The CEC will be comprised of independent and unblinded physicians that are not investigators, DSMB members or steering committee members in the trial. St. Jude Medical will appoint members of the CEC and the chairperson. St. Jude Medical may facilitate the CEC meeting, but will not be voting members.

Reportable events to be collected under this protocol will be adverse device effects outlined in sections 8.1.2-8.1.6. The CEC will base their final adjudication on the information provided on the case report forms, medical records, and their clinical knowledge and experience. The CEC will also review and classify all subject deaths under this protocol. The primary function, responsibilities and membership of the CEC will be described in detail in a CEC charter .

The Ventricular Arrhythmia Event Review Committee (VAC) will review all device detected VT and VF episodes with a stored electrogram available and non-sustained VT/VF episodes of at least 16 beats. The members of the CEC will also be members on the VAC.

VT/VF episodes with at least 4 intervals ≥ 300 ms, with 1 interval ≥ 600 ms, or with the pre-detection time lasting more than 10 seconds, will be evaluated by the VAC for ventricular arrhythmia undersensing and amount of detection delay. A clinically significant detection delay is defined as ≥ 5 seconds.

Clinical Investigational Plan

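### Section 14.1 measures detection delay only in screened episodes, and under detection settings the documents do not exclude, a delay of 5 s or more can miss the screen

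*Combined protocol and SAP*

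**What the plan says.** Section 14.1 describes two steps. First, the VAC "will review all device detected VT and VF episodes with a stored electrogram available and non-sustained VT/VF episodes of at least 16 beats". Second, a screen decides in which episodes undersensing and delay are evaluated. The screen opens with "VT/VF episodes with at least 4 intervals ≥ 300 ms, with 1 interval ≥ 600 ms, or with the pre-detection time" and the sentence ends "with the pre-detection time lasting more than 10 seconds, will be evaluated by the VAC for ventricular arrhythmia undersensing and amount of detection delay". The next sentence sets the threshold: "A clinically significant detection delay is defined as ≥ 5 seconds".

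Section 4.4.3 lists the reported measure: "Proportion of VT/VF episodes with significant detection delay assessed from device-detected VT/VF episodes (induced or spontaneous) with stored electrogram available". It stands under the introduction "The following data will also be collected", apart from the primary endpoints in sections 4.4.1 and 4.4.2.

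Section 12.2.5 freezes the data when 141 subjects have completed the 1-month visit and "a minimum of 25 subjects with at least one ventricular arrhythmia event (spontaneous or induced) are adjudicated by the Ventricular Arrhythmia Events Committee". Section 12.3 rests study success on the one safety and two efficacy endpoints.

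The text does not define pre-detection time or say how delay is calculated. It gives no detection count or rate cut-off, and does not say whether counting is cumulative or restarts after a long interval. It does not say how an episode that meets no criterion is classified. Sections 12.8 to 12.10 refer the handling of all data, missing data and exclusions to a separate statistical analysis plan.

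**The concern.** The reported proportion and the measurement behind it cover different sets of episodes. The denominator in section 4.4.3 is every device-detected episode with a stored electrogram. Delay is measured only in the subset that section 14.1 lets through. The time criterion for that subset lies above 10 s, while the delay of interest starts at 5 s, so the time criterion cannot by itself guarantee that every significant delay is measured. Whether the two interval criteria close the gap depends on how the device counts intervals, which the documents do not say.

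At stake is one descriptive result. Section 4.2 says VT/VF events are collected to characterise arrhythmia sensing and detection after MRI, and this proportion is the listed measure of detection delay. If an unmeasured delay is reported as no significant delay, the error can only lower the proportion.

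**Working it through.** The documents state no computed figure for this measure, so there is nothing to reproduce. The check is whether an episode with a delay of 5 s or more can fail all three criteria.

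**Inputs from the documents.** Section 14.1: at least 4 intervals of 300 ms or more; or 1 interval of 600 ms or more; or pre-detection time over 10 s; significant delay 5 s or more. Section 12.2.5: at least 25 subjects with an adjudicated event.

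**Assumed, because the documents do not give them.** Undelayed detection time T0 of 2 to 8 s; detection count N of 12 to 30 intervals; arrhythmia cycle length CL of 180 to 280 ms. Pre-detection time is taken as T0 plus the delay D.

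**Step 1: time criterion alone.** It misses a significant delay when D ≥ 5 s and T0 + D ≤ 10 s, that is, when D lies between 5 s and 10 − T0.

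| T0 | Delays missed by the time criterion alone |
|---|---|
| 2 s | 5 to 8 s |
| 3 s | 5 to 7 s |
| 4 s | 5 to 6 s |
| 5 s | exactly 5 s |
| over 5 s | none |

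**Step 2: add the interval criteria, with cumulative counting and a cut-off at or above 300 ms.** An episode that fails both interval criteria has at most 3 intervals of 300 to 599 ms. Their total is at most 3 × 0.599 = 1.797 s. Every shorter interval counts toward detection, so long sensed intervals cannot produce a 5 s delay without meeting an interval criterion. Nothing is missed.

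**Step 3: counting restarts after a long interval.** One undersensed beat gives a gap of 2 × CL. If it falls just before the count completes (the worst placement), it costs (N − 1) × CL + 2 × CL. With k such gaps:

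D = k × [(N − 1) × CL + 2 × CL], and pre-detection time = N × CL + D.

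| N | CL | k | Gap | D | Pre-detection time |
|---|---|---|---|---|---|
| 12 | 200 ms | 2 | 400 ms | 2 × (2.2 + 0.4) = 5.2 s | 2.4 + 5.2 = 7.6 s |
| 12 | 250 ms | 2 | 500 ms | 2 × (2.75 + 0.5) = 6.5 s | 3.0 + 6.5 = 9.5 s |
| 24 | 200 ms | 1 | 400 ms | 4.6 + 0.4 = 5.0 s | 4.8 + 5.0 = 9.8 s |

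Each row has fewer than 4 intervals of 300 ms or more, none of 600 ms, and pre-detection time below 10 s. No criterion is met, yet the delay is at least 5 s.

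**Step 4: rate cut-off shorter than 300 ms.** With an assumed cut-off of 240 ms, intervals of 240 to 299 ms neither count toward detection nor meet an interval criterion. Five seconds of them takes 5/0.299 = 16.7, so 17 intervals, up to 5/0.240 = 20.8, so 21. Whether that time is delay depends on the missing definition.

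**Step 5: what one case does to the estimate.** Taking one episode per subject in 25 subjects, 0/25 has an exact 97.5% upper limit of 1 − 0.025^(1/25) = 13.7%. For 1/25 = 4%, the exact 95% interval is 0.1% to 20.4%. This shows sensitivity to a single case, not how likely a miss is. The protocol's measure is a proportion of episodes, and a subject may contribute several.

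**The case against.** The strongest case for the plan is that the screen works as a whole. The three criteria are parallel phrases joined by a single or, so any one suffices, and the two interval criteria look directly for undersensing. Under ordinary cumulative counting with a cut-off at or above 300 ms they catch every undersensing delay of 5 s or more (step 2). A miss needs a further assumption: restarted counting, a shorter cut-off, or a delay not caused by long sensed intervals. The documents state none of these. This stands, and it limits the point to a possibility the documents leave open.

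Four stronger readings are tempting, and the text does not support them.

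- A reader might infer that all delays between 5 and 10 s go unmeasured because 10 is twice 5. The two figures measure different things: pre-detection time includes normal detection time, and the time criterion misses nothing once that exceeds 5 s. The interval criteria narrow the gap further.
- A reader might merge the first two criteria into 4 intervals of which one reaches 600 ms. Alternate-beat undersensing of a 220 ms rhythm, with sensed intervals of about 440 ms, would then escape the interval criteria. The wording does not say this. On the natural reading, four 440 ms intervals meet the 300 ms criterion.
- A reader might infer that unscreened episodes are scored as having no delay. No section says so. It is one possible consequence of the section 4.4.3 denominator, and the VAC does review all these episodes.
- A reader might link the gap to data freeze or the marketing application. The arrhythmia condition there is a count of subjects with an adjudicated event, which does not depend on the delay result.

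**Conclusion.** The point holds in a limited form. The stated rule leaves delay unmeasured in some episodes that belong to the section 4.4.3 denominator, and the documents do not show that every unmeasured delay is below 5 s. Under restarted counting, delays of 5.0 to 6.5 s with pre-detection times of 7.6 to 9.8 s meet no criterion. Under cumulative counting with a cut-off at or above 300 ms, no undersensing delay of 5 s or more is missed. Which case applies cannot be settled from the documents, so no frequency or size of bias can be given.

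The direction is known only conditionally: if unscreened episodes are reported as having no significant delay, the proportion can only be too low. The measure is descriptive, so no primary endpoint, significance level, sample size, success criterion or data-freeze condition changes. This is a minor point with a cheap improvement.

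**What to change.** Preferred: in section 14.1, have the VAC record detection delay for every device-detected VT/VF episode with a stored electrogram that it already reviews. Numerator and denominator then cover the same episodes whatever the device settings, and no rule for unscreened episodes is needed.

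Alternative: change the time criterion to a pre-detection time of 5 s or more, state that any one of the three criteria suffices, and define pre-detection time as including the delay. Since D cannot then exceed pre-detection time, every delay of 5 s or more passes the screen. An unscreened episode can be classified as having no significant delay by construction.

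Either way, section 14.1 should say how delay is calculated. The cost is a few lines there and in the VAC's procedures, plus a few more measurements on electrograms already under review. It is a measurement rule and changes nothing in patient care.

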14.2 Data Safety Monitoring Board (DSMB)

The DSMB is an independent committee responsible for monitoring study conduct, progress, and reviewing accumulated data to inform the sponsor of any circumstances that might compromise subject safety or data integrity. The DSMB will recommend at the end of each meeting whether to continue, modify or terminate the study. Membership will not include steering committee members, CEC members or site investigators for the study under review.

The primary function, responsibilities and membership of the DSMB will be described in detail in a DSMB charter.

14.3 Steering Committee

The Steering Committee will be used to advise the sponsor during a clinical study, such as in the development of the study CIP, during the conduct of the study, during data analysis and/or presentation/publication of the study results.

15.0 Investigation Suspension or Termination

15.1 Premature termination of the whole clinical study or of the clinical study in one or more investigational sites.

The Sponsor reserves the right to stop the study at any stage, with appropriate written notice to the investigator.

Possible reasons for early termination of the study by the sponsor, either at local, national or international level, may include, but are not limited to:

- The device/therapy fails to perform as intended
- Occurrence of UADE which cannot be prevented in future cases
- Sponsor's decision
- Request from Regulatory bodies
- Request of Ethics Committee(s)
- Concern for subject safety and welfare
- Failure to secure subject Informed Consent prior to any investigational activity
- Failure to report unanticipated adverse device effects within 72 hours to St. Jude Medical and the EC
- Repeated non-compliance with this CIP or the Clinical Trial Agreement
- Inability to successfully implement this CIP
- Violation of the Declaration of Helsinki 2008 (refer to Appendix C)

Clinical Investigational Plan

- Violation of applicable national or local laws and regulations
- Falsification of data, or any other breach of ethics or scientific principles
- Loss of or unaccounted use of investigational device inventory

The study will be terminated according to applicable regulations.

The investigator may also discontinue participation in the clinical study with appropriate written notice to the Sponsor.

Should either of these events occur, the investigator will return all documents to the sponsor; provide a written statement as to why the premature termination has taken place and notify the IRB/EC and/or the Competent Authority (if applicable). Follow-up for all enrolled subjects will be as per CIP requirements.

A Principal Investigator, IRB/EC or regulatory authority may suspend or prematurely terminate participation in a clinical study at the investigational sites for which they are responsible.

If suspicion of an unacceptable risk to subjects arises during the clinical study or when so instructed by the IRB/EC or regulatory authority, St. Jude Medical may suspend the clinical study as appropriate while the risk is assessed. St. Jude Medical will terminate the clinical study if an unacceptable risk is confirmed.

St. Jude Medical will consider terminating or suspending the participation of a particular investigational site or investigator in the clinical study if monitoring or auditing identifies serious or repeated deviations on the part of an investigator.

If suspension or premature termination occurs, the terminating party will justify its decision in writing and promptly inform the other parties with whom they are in direct communication. The Principal Investigator and St. Jude Medical will keep each other informed of any communication received from IRB/EC or regulatory authority.

If for any reason St. Jude Medical suspends or prematurely terminates the study at an individual investigational site, St. Jude Medical will inform the responsible regulatory authority, as appropriate, and ensure that the IRB/EC are notified, either by the Principal Investigator or by St. Jude Medical. If the suspension or premature termination was in the interest of safety, St. Jude Medical will inform all other Principal Investigators.

If suspension or premature termination occurs, St. Jude Medical will remain responsible for providing resources to fulfill the obligations from the CIP and existing agreements for following up the subjects enrolled in the clinical study, and the Principal Investigator or

Clinical Investigational Plan

authorized designee will promptly inform the enrolled subjects at his/her investigational site, if appropriate.

15.2 Resuming the study after temporary suspension

When St. Jude Medical concludes an analysis of the reasons for the suspension, implements the necessary corrective actions, and decides to lift the temporary suspension, St. Jude Medical will inform the Principal Investigators, IRB/EC, or regulatory authority, where appropriate, of the rationale, providing them with the relevant data supporting this decision.

Concurrence will be obtained before the clinical study resumes from the IRB/EC or regulatory authority where appropriate.

If subjects have been informed of the suspension, the Principal Investigator or authorized designee will inform them of the reasons for resumption.

15.3 Study Conclusion

The study will be concluded when:

- All sites are closed AND
- The Final report generated by St. Jude Medical has been provided to sites or St. Jude Medical has provided formal documentation of study closure

16.0 Publication Policy

The results of the clinical study will be submitted, whether positive or negative for publication.

A 'Publication Agreement' will be signed between the Principal Investigator and the Sponsor either as a separate Publication Agreement or within the Clinical Trial Agreement.

For more information on publication guidelines, please refer to the International Committee of Medical Journal Editors (ICMJE) on www.icmje.org.

Upon receiving IDE approval from the FDA, this clinical study will be registered on ClinicalTrials.gov. A full report of the pre-specified outcomes, including any negative outcomes, will be made public through the ClinicalTrials.gov website according to the requirements of Section 801 of the FDA Amendments Act. If this clinical study is terminated early, the Sponsor will make every effort to accelerate the release of the pre-specified outcomes through the ClinicalTrials.gov website.

Clinical Investigational Plan

17.0 Bibliography

A literature search was conducted to obtain information relevant to implanted active medical devices, including ICDs, and MRI scanning to characterize and understand the effects of MRI scanning on ICDs. A list of the bibliographic references pertaining to this study can be found in the References section of this document.

Clinical Investigational Plan

Appendix A: Abbreviations

Abbreviation	Term
ADE	Adverse Device Effect
AE	Adverse Event
ANZ	Australia – New Zealand
ASADE	Anticipated Serious Adverse Device Effect
CA	Competent Authority
CCI	Clinical Coordination Investigator
CEC	Clinical Events Committee
CIP	Clinical Investigational Plan
CRF	Case Report Form
CPRB	Clinical Project Review Board
DMP	Data Management Plan
DSMB	Data Safety Monitoring Board
EC	Ethics Committee
ECG	Electrocardiogram
eCRF	Electronic Case Report Form
EDC	Electronic Data Capture
EMEA	Europe, Middle East, Africa
GP	General Practitioner
IB	Investigator Brochure
ICMJE	International Committee of Medical Journal Editors
IRB	Institutional Review Board
ISB	Investigator Site Binder
ISO	International Organization for Standardization
MP	Monitoring Plan
NA	Not Applicable
OUS	Outside the United States
PI	Principal Investigator
POA	Power of Attorney
RDC	Remote Data Capture
SADE	Serious Adverse Device Effect
SAE	Serious Adverse Event
SC	Steering Committee
SJM	St. Jude Medical
USADE	Unanticipated Serious Adverse Device Effect
WMA	World Medical Association

Clinical Investigational Plan

Appendix B: CIP Revision History

Revision History

Amendment Number	Version	Date	Rationale	Details
Not Applicable	A	06Nov2015	First release of CIP.	First document controlled version of protocol submitted to FDA 14Nov2015.
Not Applicable	B	11Jan2016	Protocol revised based on feedback from FDA	
 • Usage of registered trademark and unregistered trademark symbols revised for applicable devices • Modified the synopsis and protocol to indicate that the PMA will be submitted to FDA when both the minimum sample size for each endpoint has been met and a minimum of 25 subjects with at least one ventricular arrhythmia episode has been adjudicated by the Ventricular Arrhythmia Events Committee. • Added note to synopsis stating that all references to MRI scan in the protocol refer to the study MRI scan • Clarified that ventricular events consist of Ventricular tachycardia (VT) and Ventricular Fibrillation (VF). • Added wording that VT/VF events will include follow up visits where R-wave sensing is impaired. • Added additional data to be collected in Section 4.4.3 to include the number of subjects that returned to usual programming after the MRI scan and the number of subjects, if any, experiencing delays in reprogramming • Added wording within the Study Procedures and Data Collection table to clarify that among sites participating in the sub study, subjects will be approached with both the main study and sub study consents. • Added MRI Survey Form and Induction Testing Form to Table 5. • Removed “if MRI scan visit does not

Clinical Investigational Plan

Amendment Number	Version	Date	Rationale	Details
				
occur the same day as baseline” when referring to the Hazard checklist required as part of Pre-MRI Scan testing.
 
 • Added a Non-study MRI Scan form (if applicable) to account for medically required MRI scans. • Added wording for sites to use the automatically obtained pacing capture threshold from most recent archival data as a substitute for the in-clinic threshold, if a high ventricular rate was present during in-clinic interrogation. • Updated Study Flow Chart • Clarified Subject Inclusion criteria #1 to reinforce that eligible patients can include those with the Durata/Optisure lead ≥ 60 days • Added wording within the VT/VF Data Collection Effort section to indicate that if a subject consented in the main study has impaired R wave sensing after the MRI scan visit or other clinical reason for induction testing, then the physician may choose to complete induction testing for that subject. • Within Pre-scan device assessment, removed typo regarding Bipolar lead impedance. • Added wording to clarify when the MRI Parameters table should be used. • Added wording and updated the definition of a reproducibly occurring arrhythmia in MRI Scan section 6.5.2.1. • Added wording in Scheduled Follow Up section to clarify that all subjects will be evaluated for spontaneous VT/VF episodes. • Added wording in Scheduled Follow Ups section to clarify that a minimum of 25 subjects with at least one VT/VF

Clinical Investigational Plan

Amendment Number	Version	Date	Rationale	Details
				
episode will be adjudicated by the Ventricular Arrhythmia Events Committee.
 
 • Added a note in the Post-Scan Testing section to reinforce that MRI settings must be disabled to ensure that tachyarrhythmia therapy is turned back on. • Added Section 6.10 for Non-study MRI scans • Added wording in Section 6.12 to clarify the duration of sub study data collection. • Added Section 8.2.3 to include a Preliminary Report after the first 20 subjects complete the one month post MRI scan visit and/or if at least 5 subjects experience a worsening of pacing capture threshold, defined by the primary endpoint. • Added note in section 12 specifying that references to MRI refer to the study MRI scan. • Added Section 12.2.5 for Analysis • Added wording to include a combined committee (Clinical Events Committee/Ventricular Arrhythmia Event Review Committee) to review adverse device effects, deaths and ventricular arrhythmia events. • Revised Appendix F: MRI Screening Form to update the numbering of the questions and addition of the subject ID example. • Added site name, subject ID, and date of completion to Appendix G: MRI Hazard Checklist. • Modified Appendix I: Sample Informed Consent & Sub study consent.

Clinical Investigational Plan

